4 OBJECTIVES AND ENDPOINTS

Table 4-1: Objectives and Endpoints

Objectives	Endpoints

The primary objective of this study is to characterize the PK and assess the safety and tolerability of BMS-986205 administered alone and in combination with nivolumab in Chinese participants with advanced malignant tumors.	
PK parameters Incidence of AEs, SAEs, AEs leading to discontinuation, deaths, and laboratory abnormalities

The secondary objectives of this study are:
 
To characterize the pharmacodynamic activity of BMS-986205 administered alone and in combination with nivolumab.To characterize the immunogenicity of nivolumab when administered in combination with BMS-986205.To investigate the preliminary anti-tumor activity of BMS-986205 administered in combination with nivolumab in advanced malignant tumors.	
Incidence of anti-drug antibodies (ADA) to nivolumab; measurement of serum kynurenine and tryptophan levelsORR, best overall response (BOR) and duration of response (DOR) as assessed per Response Evaluation Criteria in Solid Tumors (RECIST) v1.1 by investigator

5 STUDY DESIGN

5.1 Overall Design

This is a Phase 1/2, open-label study of BMS-986205 administered as a monotherapy and in combination with nivolumab in participants with advanced malignant solid tumors.

Treatment will start with a 2-week monotherapy lead-in (Cycle 0) whereby

BMS-986205 100 mg oral daily dose must be administered with a meal at approximately the same time each day.

Participants will then proceed to receive the combination of nivolumab and BMS-986205. Nivolumab will be administered at a dose of 480 mg IV Q4W.

Cycle 0

[figure not shown]
Participants will start with Cycle 0, which is a 2-week BMS-986205 monotherapy lead-in, with a 100-mg oral daily dose. Participants who have received at least 75% of doses in Cycle 0 will be eligible to proceed to receive the combination of nivolumab and BMS-986205 (Cycle 1).

The following AEs will prohibit a participant from proceeding to combination with nivolumab (Cycle 1):

- Grade 2 or higher immune-related AEs (irAEs) considered related to BMS-986205 (eg, immune-mediated pneumonitis, colitis, hepatitis, nephritis, and renal dysfunction) with the exception of immune-mediated hypothyroidism and hyperthyroidism
- Grade 2 AST and ALT elevations that do not resolve to Grade 1 or baseline within 1 week
- \geq Grade 3 elevation of AST, ALT, or total bilirubin that persists for \geq 7 days
- Grade 2 AST or ALT elevation with symptomatic liver inflammation (eg, right upper quadrant tenderness, jaundice, pruritus)
- AST or ALT $> 3\times$ upper limit of normal (ULN) and concurrent total bilirubin $> 2\times$ ULN without initial findings of cholestasis (elevated serum alkaline phosphatase, eg, findings consistent with Hy's law or FDA definition of potential drug-induced liver injury [DILI])
- Grade 2 or greater episcleritis, uveitis, or iritis
- Any other Grade 2 eye pain or blurred vision that does not respond to topical therapy and does not improve to Grade 1 severity within 2 weeks OR requires systemic treatment
- Grade 3 or greater uveitis, pneumonitis, bronchospasm, neurologic toxicity, hypersensitivity reaction, or infusion reaction of any duration requires discontinuation
- Any Grade 3 or greater non-dermatologic, non-hepatic, non-hematologic toxicity with the following specific EXCEPTIONS:
 - Grade 3 or Grade 4 electrolyte abnormalities that are not complicated by associated clinical adverse experiences, last less than 48 hours and either resolve spontaneously or respond to conventional medical intervention
 - Grade 3 nausea, vomiting, or diarrhea that lasts less than 48 hours, and either resolves spontaneously or responds to conventional medical intervention
 - Isolated Grade 3 elevation of amylase or lipase not associated with clinical or radiographic evidence of pancreatitis
 - Isolated Grade 3 fever not associated with hemodynamic compromise (eg, hypotension, clinical or laboratory evidence of impaired end-organ perfusion)
 - Grade 3 endocrinopathy that is well-controlled by hormone replacement
 - Grade 3 tumor flare (defined as pain, irritation, or rash that localizes to site of known or suspected tumor)
 - Grade 3 fatigue
- Grade 3 rash if no improvement (ie, resolution to \leq Grade 1) after a 1- to 2-week dose delay.
- Grade 4 rash of any duration
- Methemoglobin levels $\geq 15\%$ and study-drug related
- Grade 4 neutropenia ≥ 5 days in duration and study-drug related
- Grade 4 thrombocytopenia or Grade 3 thrombocytopenia with bleeding (study-drug related), or any requirement for platelet transfusion (study-drug related)
- Grade ≥ 3 febrile neutropenia for 48 hours, study-drug related
- Grade ≥ 3 hemolysis (ie, requiring transfusion or medical intervention such as steroids), study-drug related
- Grade 4 anemia not explained by underlying disease (study-drug related)

The study design schematic is presented in [Figure 5.1-1](#).

Figure 5.1-1: Study Design Schematic

Treatment may continue from Cycle 0 (2 weeks) until 50 weeks (or up to a total maximum of 98 weeks if applicable), disease progression, or withdrawal of consent.

In addition, cohort may be expanded in this study to gather additional safety, tolerability, PK, pharmacodynamics, and preliminary efficacy information regarding BMS-986205 in combination with nivolumab in certain tumor type(s).

Participants will complete up to 3 phases of the study: Screening, Treatment, and Clinical/Safety Follow-up, as described below.

Screening

The screening phase will last for up to 28 days. Screening begins by establishing the participant's initial eligibility and signing the informed consent form (ICF).

Treatment

The treatment phase consists of the 2-week monotherapy lead-in (Cycle 0) and up to twelve 4-week combination therapy cycles. The 2-week lead-in treatment consists of a single oral daily dose of BMS-986205. The combination therapy cycles are comprised of an oral daily dose of BMS-986205 and one dose of nivolumab administered intravenously Q4W on Day 1 of each treatment cycle up to 12 cycles. Total study treatment period is up to 50 weeks.

Following every two combination therapy treatment cycles (8 weeks) starting with Cycle 1, the decision to treat a participant with additional cycles of study therapy will be based on radiological tumor assessments (initial evaluation performed at baseline, end of Cycle 2, and every 8 weeks). Assessments of PR and CR must be confirmed at least 4 weeks following initial assessment. Tumor progression or response endpoints will be assessed using RECIST v1.1 criteria for solid tumors ([Appendix 5](#)).

Treatment beyond progression may be allowed in select participants with initial RECIST v1.1 disease progression (PD) after discussion and agreement with the BMS medical monitor (with proper documentation in the Trial Master File) that the benefit/risk assessment favors continued administration of study therapy (eg, participants are continuing to experience clinical benefit as assessed by the investigator, tolerating treatment, and meeting other criteria specified in [Section 8.1.2](#)).

Participants with a response of stable disease (SD), PR, or CR at the end of a given cycle will continue to the next treatment cycle. Participants will generally be allowed to continue study therapy until the first occurrence of either: 1) completion of the maximum number of 12 cycles; 2) PD; 3) clinical deterioration suggesting that no further benefit from treatment is likely; 4) intolerance to therapy; or 5) the participant meets criteria for discontinuation of study therapy as outlined in [Section 7.4.4](#). Individual participants with confirmed CR will be given the option to discontinue study therapy on a case-by-case basis after specific consultation and agreement between the investigator and BMS medical monitor in settings where benefit/risk justify discontinuation of study therapy.

In all parts of this study, all participants will be treated for 48 weeks of BMS-986205 in combination with nivolumab unless criteria for study drug discontinuation are met earlier ([Section 7.4.4](#)). All participants completing approximately 48 weeks of combination study therapy with ongoing disease control (CR, PR, or SD) may be eligible for an additional 48 weeks of study therapy at the originally assigned dose regimen beyond the initial 48 weeks, on a case-by-case basis, after careful evaluation and discussion with the BMS medical monitor to determine whether the benefit/risk ratio supports administration of further study drug. Subjects whose last assessment of the initial 48-week period shows PD will also be eligible to continue to additional cycles if they are still deriving clinical benefit, as per the guidance of treatment beyond progression ([Section 8.1.2](#)). Upon completion of 48 weeks of combination treatment (or up to a maximum of 96 weeks if applicable), all subjects will enter the Clinical/Safety Follow-Up period.

Clinical/Safety Follow-Up

Upon completion of 48 weeks of combination treatment (or up to a maximum of 96 weeks if applicable), all participants will enter the Clinical/Safety Follow-Up period after the decision is made to discontinue the participant from treatment (eg, at end of treatment [EOT]).

For participants who complete all scheduled cycles of therapy, the EOT visit will be the same as the last scheduled and completed on-treatment visit, and the start of the Week 1 Clinical/Safety Follow-Up visit. For participants who do not complete all scheduled cycles of therapy, the EOT visit will be the most recent on-treatment visit (with all available safety and response data) and does not need to be repeated, and will be considered the start of the Week 1 Clinical/Safety Follow-Up visit.

Participants who discontinue the treatment phase will enter the Clinical/Safety Follow-Up period. Participants must be followed for at least 100 days after the last dose of study therapy or 30 days if participant only received BMS-986205. Follow-up visits should occur at Days 30, 60, and 100 (\pm 10 days) after the last dose of study therapy or should coincide with the date of discontinuation (\pm 10 days) if date of discontinuation is greater than 30 days after the last dose of study therapy to monitor for AEs. All participants will be required to complete one (if participant only received BMS-986205) or three Clinical/Safety Follow-Up visits regardless of whether they start a new anti-cancer therapy, except those participants who withdraw consent for study participation.

5.1.1 Data Monitoring Committee and Other External Committees

[figure not shown]
Not applicable.

[figure not shown]
5.2 Number of Participants

[figure not shown]
A sample size of 12 PK evaluable subjects is proposed for this study. Based on preliminary PK results from Study CA017003 cohorts 25 to 200 mg, assuming the inter-subject coefficient of variation (CV) for AUC24 is 42%, a sample size of 12 PK evaluable subjects will be sufficient for the point estimates of the mean PK parameter to fall within 80% to 125% of the true value, with 91% confidence level. Assuming the inter-subject CV for Cmax is 29%, a sample size of 12 PK evaluable subjects will be sufficient for the point estimates of the mean PK parameter to fall within 80% to 125% of the true value, with 98% confidence level. Twelve subjects will provide 90% probability of observing at least 1 occurrence of a specific AE that would occur with an 18% incidence in the population. If a participant discontinues before or at Cycle 1 Day 1, an additional patient will be enrolled to ensure 12 PK evaluable participants are to be enrolled in this study.

5.3 End of Study Definition

The start of the trial is defined as first visit for first participant screened. End of trial is defined as the last visit or scheduled procedure shown in the Schedule of Activities for the last participant. Study completion is defined as the final date on which data for the primary endpoint was or is expected to be collected, if this is not the same.

6 STUDY POPULATION

For entry into the study (prior to C0D1), the following criteria MUST be met.

6.1 Inclusion Criteria

1) Signed Written Informed Consent

- a) The participant must sign and date an IRB/IEC-approved ICF prior to the performance of any study related procedures that are not considered part of standard of care.

2) Type of Participant and Target Disease Characteristics

- a) Participants must have histologic or cytological confirmation of a malignancy (solid tumor) that is advanced (metastatic and/or unresectable) with measurable disease per RECIST v1.1 (see [Appendix 5](#)).
- b) Participants must have received, and then progressed or been intolerant to at least one standard treatment regimen in the advanced or metastatic setting, if such a therapy exists. Participants who refuse or are ineligible for standard therapy will be allowed to enroll provided refusal/ineligibility is documented.
- c) Participants must have an Eastern Cooperative Oncology Group performance status of ≤ 1 .
- d) Participants must be able to swallow pills or capsules.
- e) Participants must present with at least one lesion with measurable disease as defined by RECIST v1.1 for solid tumors for response assessment. Participants with lesions in a previously irradiated field as the sole site of measurable disease will be permitted to enroll provided the lesion(s) have demonstrated clear progression and can be measured accurately.
- f) Participants with prior exposure to therapy with any agent specifically targeting checkpoint pathway inhibition other than PD-1 or PD-L1 (such as; anti-PDL-2, anti-lymphocyte activation gene 3 [LAG-3], and anti CTLA-4 antibody) are permitted after a washout period of any time greater than 4 weeks from the last treatment. Participants with prior therapy with any agent specifically targeting T-cell costimulation pathways such as anti-glucocorticoid-induced tumor necrosis factor receptor (TNFR) family related gene antibody, anti-CD137, anti-OX40 antibody, are permitted after a washout period of any time greater than 4 weeks from the last treatment.
 - i) Participants who experienced prior Grade 1 to 2 checkpoint therapy-related immune-mediated AEs must have confirmed recovery from these events at the time of study entry, other than endocrinopathies treated with supplementation, as documented by resolution of all related clinical symptoms, abnormal findings on PE, and/or associated laboratory abnormalities. Where applicable, these participants must also have completed steroid tapers for treatment of these AEs by a minimum of 14 days prior to commencing treatment with study drug.
 - ii) Eligibility of participants with prior \geq Grade 3 checkpoint therapy-related immune AEs, will be considered on a case-by-case basis after discussion with the medical monitor (eg, asymptomatic isolated Grade 3 lipase elevations without clinical or radiological features of pancreatitis will be permitted to enroll).
- g) Prior palliative radiotherapy must have been completed at least 2 weeks prior to first dose of study drug. Participants with symptomatic tumor lesions at baseline that may require palliative radiotherapy within 4 weeks of first dose of study drug are strongly encouraged to receive palliative radiotherapy prior to enrollment.
- h) Participants must have blood methemoglobin levels within the ULN.
- i) Participants must have adequate marrow function for participants with solid tumor histologies as defined by the following:
 - White blood cells (WBC) $\geq 2000/\mu\text{L}$ (stable off any growth factor within 4 weeks of first study drug administration)

- Neutrophils $\geq 1500/\mu\text{L}$ (stable off any growth factor within 4 weeks of first study drug administration)
- Platelets $\geq 100 \times 10^3/\mu\text{L}$ (transfusion to achieve this level is not permitted within 2 weeks of first study drug administration)
- Hemoglobin $\geq 8.5 \text{ g/dL}$ (transfusion to achieve this level is not permitted within 2 weeks of first study drug administration)
- j) Participants must have adequate other organ function as defined by the following:
 - i) ALT and AST $\leq 3 \times$ institutional ULN
 - ii) Total bilirubin $\leq 1.5 \times$ institutional ULN (except participants with Gilbert's Syndrome who must have normal direct bilirubin)
 - iii) Normal thyroid function, subclinical hypothyroidism (thyroid-stimulating hormone [TSH] $< 10 \text{ mIU/mL}$) or have controlled hypothyroidism on appropriate thyroid supplementation
 - iv) Serum creatinine $\leq 1.5 \times$ ULN or creatinine clearance (CrCl) $\geq 40 \text{ mL/min}$ (measured using the Cockcroft-Gault formula below):
$$\text{Female CrCl} = \frac{(140 - \text{age in years}) \times \text{weight in kg} \times 0.85}{72 \times \text{serum creatinine in mg/dL}}$$
$$\text{Male CrCl} = \frac{(140 - \text{age in years}) \times \text{weight in kg} \times 1.00}{72 \times \text{serum creatinine in mg/dL}}$$
- k) Ability to comply with treatment, PK and pharmacodynamic sample collection, and required study follow-up.
- l) Life expectancy ≥ 3 months.

3) Age and Reproductive Status

- a) Participants must be male and female, age ≥ 18 years at the time of informed consent.
- b) Women of childbearing potential (WOCBP) must have a negative serum or urine pregnancy test (minimum sensitivity 25 IU/L or equivalent units of HCG) within 24 hours prior to the start of study treatment.
- c) Women must not be pregnant or breastfeeding.
- d) WOCBP must agree to follow instructions for method(s) of contraception ([Appendix 4](#)) for the duration of treatment with study treatment(s) plus 5 months (approximately 23 weeks) post-treatment completion.
- e) Males who are sexually active with WOCBP must agree to follow instructions for method(s) of contraception ([Appendix 4](#)) for the duration of treatment with study treatment(s) plus an additional 7 months (approximately 31 weeks) post-treatment completion. In addition, male participants must be willing to refrain from sperm donation during this time.
- f) Males who are sexually active with WOCBP must agree to use a condom (see [Appendix 4](#)) for the duration of treatment with study treatment plus 7 months after the last dose of the study treatment (ie, 90 days [duration of sperm turnover] plus the time required for nivolumab to undergo approximately 5 half-lives). In addition, male subjects must be willing to refrain from sperm donation during this time. This criteria applies to azoospermic males as well.

g) WOCBP who are continuously not heterosexually active are also exempt from contraceptive requirements, but still must undergo pregnancy testing as described in this section.

Investigators shall counsel WOCBP and male participants who are sexually active with WOCBP on the importance of pregnancy prevention and the implications of an unexpected pregnancy. Investigators shall advise on the use of highly effective methods of contraception ([Appendix 4](#)) that have a failure rate of < 1% when used consistently and correctly. It is important to note that contraceptive methods that rely on hormones are not considered highly effective for subjects receiving BMS-986205.

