Chemistry (Excluding Liver Function Test LFTs))		X	Includes assessments for sodium, potassium, chloride, total serum calcium, magnesium, bicarbonate/carbon dioxide, phosphorus, blood urea nitrogen (BUN), creatinine, creatinine clearance, C-reactive protein, fasting glucose, total protein, albumin, amylase, lipase, uric acid, ferritin, and lactate dehydrogenase (LDH).
G6PD Deficiency Testing	X		
Methemoglobin		X	Methemoglobin levels to be assessed on arterial or venous blood sample
Reticulocyte counts and haptoglobin		X	At baseline and reflex when methemoglobin is elevated over upper limit of normal [ULN]). Additional samples as clinically indicated.
CBC with Differential and Platelets		X	Includes hemoglobin, hematocrit, platelet count, and total leukocyte count including differential.
LFT Assessments		X	Includes aspartate aminotransferase (AST) and alanine aminotransferase (ALT), total bilirubin, direct bilirubin (only if total bilirubin is elevated), alkaline phosphatase, and gamma-glutamyl transferase (GGT) (only when alkaline phosphatase increases to \geq Grade 2).
PT/aPTT/INR		X	
Urinalysis		X	Refer to Table 9.4.1-1
Thyroid Function Tests		X	TSH with free thyroxine (T4) and triiodothyronine (T3)
Serology	X		Refer to Table 9.4.1-1
Pregnancy Test		X	Women of childbearing potential (WOCBP) only at screening and within 24 hours prior to dosing.
Follicle Stimulating Hormone (FSH)	X		If needed to document postmenopausal status as defined in Appendix 4 .
Adverse Event Reporting			
Monitor for Serious Adverse Events	X	X	All serious adverse events (SAEs) must be collected from the date of subject's written consent until 100 days post discontinuation of nivolumab (or 30 days if participant only received BMS-986205), or participant's participation in the study if the last scheduled visit occurs

Table 2-1: Screening Procedural Outline (CA017076)

Procedure	D -28 to D -1	D -14 to D -1	Notes
			at a later time. SAEs reported in the BMS EDC tool should be approved within 5 business days of entry.
Baseline Efficacy Assessments			
Diagnostic Imaging	X		Computed tomography (CT) with contrast is the preferred modality (Magnetic resonance imaging [MRI] if CT is not feasible). Assessment should include the chest/abdomen/pelvis at a minimum; and should include other anatomic regions as indicated by individual participant disease histories.

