- h) Participants must not have any anti-cancer therapy (eg, chemotherapy, biologics, vaccines, or hormonal treatment) including investigational drugs within 4 weeks prior to the first dose of study drug administration, except for non-cytotoxic therapies, for which at least

4 weeks or 5 half-lives (whichever is shorter) must have elapsed between last dose and first treatment with any study drugs; if 5 half-lives is shorter than 4 weeks, agreement with the Medical Monitor must be obtained.

- i) Participants must not have had prior therapy with an IDO inhibitor.
- j) Participants must not have active, known, or suspected autoimmune disease. Participants with vitiligo, type 1 diabetes mellitus, residual hypothyroidism due to autoimmune condition only requiring hormone replacement, euthyroid participants with a history of Grave's disease (participants with suspected autoimmune thyroid disorders must be negative for thyroglobulin and thyroid peroxidase antibodies and thyroid stimulating immunoglobulin prior to first dose of study drug), psoriasis not requiring systemic treatment, or conditions not expected to recur in the absence of an external trigger are permitted to enroll.
- k) Participants must not have a condition requiring systemic treatment with either corticosteroids (> 10 mg daily prednisone equivalents) or other immunosuppressive medications within 14 days of study drug administration.
Note: Treatment with a short course of steroids (< 5 days) up to 7 days prior to initiating study drug is permitted.
- l) Participants must not require daily supplemental oxygen.
- m) Participants must not have uncontrolled or significant cardiovascular disease including, but not limited to, any of the following:
 - i) Myocardial infarction or stroke/transient ischemic attack within the past 6 months.
 - ii) Uncontrolled angina within the past 3 months.
 - iii) Any history of clinically significant arrhythmias (such as ventricular tachycardia, ventricular fibrillation, or Torsades de pointes).
 - iv) QT interval corrected for heart rate using Fridericia's formula (QTcF) prolongation ≥ 480 msec.
 - v) History of other clinically significant heart disease (eg, cardiomyopathy, congestive heart failure with New York Heart Association functional classification III-IV, pericarditis, significant pericardial effusion, or myocarditis).
 - vi) Cardiovascular disease-related requirement for daily supplemental oxygen therapy.

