APPENDIX 4 WOMEN OF CHILDBEARING POTENTIAL DEFINITIONS AND METHODS OF CONTRACEPTION

DEFINITIONS

Woman of Childbearing Potential (WOCBP)

A woman is considered fertile following menarche and until becoming post-menopausal unless permanently sterile. Permanent sterilization methods include hysterectomy, bilateral salpingectomy, and bilateral oophorectomy.

Women in the following categories are not considered WOCBP

- Premenarchal
- Premenopausal female with 1 of the following:
 - Documented hysterectomy
 - Documented bilateral salpingectomy
 - Documented bilateral oophorectomy

Note: Documentation can come from the site personnel's review of the participant's medical records, medical examination, or medical history interview.

- Postmenopausal female
 - A postmenopausal state is defined as 12 months of amenorrhea in a woman over age 45 years in the absence of other biological or physiological causes. In addition, females under the age of 55 years must have a serum follicle stimulating hormone, (FSH) level > 40 mIU/mL to confirm menopause.

CONTRACEPTION GUIDANCE FOR FEMALE PARTICIPANTS OF CHILD BEARING POTENTIAL

One of the highly effective methods of contraception listed below is required during study duration and until the end of relevant systemic exposure, defined as 5 months after the end of study treatment.*

Highly Effective Methods That Are User Independent

- Non-hormonal intrauterine devices (IUDs) such as ParaGard®
- Bilateral tubal occlusion
- Vasectomized partner

A vasectomized partner is a highly effective contraception method provided that the partner is the sole male sexual partner of the WOCBP and the absence of sperm has been confirmed. If not, an additional highly effective method of contraception should be used.

- Sexual abstinence

Sexual abstinence is considered a highly effective method only if defined as refraining from heterosexual intercourse during the entire period of risk associated with the study drug. The reliability of sexual abstinence needs to be evaluated in relation to the duration of the study and the preferred and usual lifestyle of the participant.

- It is not necessary to use any other method of contraception when complete abstinence is elected.
- WOCBP participants who choose complete abstinence must continue to have pregnancy tests, as specified in [Section 2](#).

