#### Abnormal Thyroid Function Test

The number of subjects with the following laboratory abnormalities from on-treatment evaluations will be summarized:

- TSH value > ULN and
  - with baseline TSH value  $\leq$  ULN
  - with at least one FT3/FT4 test value < LLN within 2-week window after the abnormal TSH test
  - with all FT3/FT4 test values  $\geq$  LLN within 2-week window after the abnormal TSH test
  - with FT3/FT4 missing within 2-week window after the abnormal TSH test
- TSH < LLN and
  - with baseline TSH value  $\geq$  LLN
  - with at least one FT3/FT4 test value > ULN within 2-week window after the abnormal TSH test
  - with all FT3/FT4 test values  $\leq$  ULN within 2-week window after the abnormal TSH test
  - with FT3/FT4 missing within 2-week window after the abnormal TSH test

A by-subject listing of these specific abnormalities will be provided.

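### The TSH cap for subclinical hypothyroidism in inclusion 2j(iii) is written in mIU/mL, which puts it at 10,000 mIU/L and leaves the only numeric thyroid limit at entry without effect

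*Protocol*

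**What the plan says.** Protocol 6.1, inclusion 2j(iii), lists three thyroid states that allow entry: normal function; "subclinical hypothyroidism (thyroid-stimulating hormone [TSH] $< 10 \text{ mIU/mL"; or to "have controlled hypothyroidism on appropriate thyroid supplementation". Only the second carries a number.

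No other text supplies or corrects a TSH limit:

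- **Protocol 6.2, exclusion 2j (autoimmune disease)** allows "residual hypothyroidism due to autoimmune condition only requiring hormone replacement" and gives no TSH value.
- **Protocol Table 2-1** schedules "TSH with free thyroxine (T4) and triiodothyronine (T3") at screening, without a unit or range. Table 9.4.1-1 is equally silent.
- **The synopsis** does not repeat the criterion.
- **SAP 7.6.10.5 (Abnormal Thyroid Function Test)** judges TSH only against the laboratory's limits, for example "with baseline TSH value $\leq$ ULN".

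The same unit appears once more, for a different hormone: Appendix 4 requires an FSH "level > 40 mIU/mL to confirm menopause".

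Protocol Section 6 makes the entry criteria mandatory, and the end of 6.2 insists that participants meet all of them in full.

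**The concern.** A mandatory eligibility number should work when it is applied literally. If TSH is read on the mIU/L scale (an assumption, since the documents name no other TSH unit), a cap in mIU/mL lies far above any value a laboratory would plausibly return. It then cannot separate a participant with a slightly raised TSH from one with a much higher TSH, provided both count as subclinical.

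No scheduled thyroid test soon afterwards makes up for this. Protocol Table 2-2 has none in Cycle 0, and Table 2-3 starts them at Cycle 3 Day 1. Any programmed eligibility check that copied the written unit would flag nobody, and SAP 7.2 plans listings of significant deviations that may be programmable.

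**Working it through.** **Inputs**

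- Written limit: TSH < 10 mIU/mL (Protocol 6.1, 2j(iii)).
- Assumed, not in the documents: an upper normal limit for TSH of 4 to 5 mIU/L, and trial values from 10 to 1,000 mIU/L.

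The plan derives the limit from nothing, so there is no calculation of its own to reproduce. The check is a unit conversion followed by a comparison.

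**Step 1. Convert the written limit.**

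10 mIU/mL × 1,000 mL/L = 10,000 mIU/L.

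On the alternative scale, 1 microIU/mL = 0.001 mIU/mL = 1 mIU/L, so 10 microIU/mL = 10 mIU/L. The two readings differ by 10,000 / 10 = 1,000.

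**Step 2. Compare with the assumed upper normal limit.**

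- At 4 mIU/L: 10,000 / 4 = 2,500 times.
- At 5 mIU/L: 10,000 / 5 = 2,000 times.

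**Step 3. Apply the written limit to a range of assumed TSH values.**

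| Assumed TSH (mIU/L) | In mIU/mL | Below 10 mIU/mL? | Written limit ÷ value |
|---|---|---|---|
| 10 | 0.01 | yes | 1,000 |
| 50 | 0.05 | yes | 200 |
| 100 | 0.1 | yes | 100 |
| 500 | 0.5 | yes | 20 |
| 1,000 | 1.0 | yes | 10 |

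Even the largest value tried is a tenth of the written limit.

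**Step 4. See what the rest of the criterion still does.** The number qualifies the subclinical state only. A participant with untreated overt hypothyroidism fits none of the three states, whatever the unit, and T4 and T3 are measured with TSH at screening, so the distinction can be made. The unit matters for a participant with normal T4 and T3 and a TSH above 10 mIU/L. That person qualifies as written and would not qualify if 10 was meant in mIU/L.

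**Step 5. Look for a later scheduled test.** Cycle 0 lasts 2 weeks and Cycles 1 and 2 last 4 weeks each. The first scheduled on-treatment thyroid test therefore falls about 2 + 4 + 4 = 10 weeks after the first dose of BMS-986205, and after two nivolumab doses.

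**Step 6. Check for a text-extraction fault.** A micro sign misread as the letter m would produce the same string. In the same inclusion list, however, the micro sign survives: "Neutrophils $\geq 1500/\mu\text{L". A misreading is therefore unlikely but not excluded, and the source page settles it.

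**The case against.** The strongest case against is that this is a one-letter slip in a parenthesis, which an experienced investigator would read past, and that little follows from it. Much of that stands.

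- **Overt disease.** A reader might infer that the criterion admits untreated overt hypothyroidism. It does not: the words normal, subclinical and controlled govern entry, and screening T4 and T3 let the site apply them.
- **Differences between sites.** A reader might infer that some sites would silently correct the unit and others would not. Protocol Appendix 2, under the clinical study report, describes a single-site protocol. The SAP's planned enrollment table by country and site does not show otherwise.
- **Distorted thyroid rates.** A reader might infer that each extra entrant shifts a thyroid abnormality rate by 8.3 percentage points. That figure is just 1/12, the weight of any one of 12 participants, and is not an effect of the unit. The SAP thyroid rows use ULN and LLN, not the entry limit. One row is restricted to participants whose baseline TSH is not raised, so someone entering with a raised TSH is not counted there as a new abnormality. Raised baselines are also expected with the unit corrected, because subclinical disease is admitted either way.
- **Outside knowledge.** The statement that the cap has no effect needs a TSH range that the documents do not give. It is therefore put here as an assumption with its range shown.

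None of this restores the number. It is the only TSH limit in either document, it belongs to a criterion that must be met, and nothing elsewhere overrides its unit.

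**Conclusion.** The concern holds in a narrow form. The conversion to 10,000 mIU/L is exact. That the cap excludes nobody is conditional: it holds for every assumed TSH value up to 1,000 mIU/L. That the figure is 1,000 times too high is also conditional, on 10 having been meant in mIU/L, which only the sponsor can confirm.

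The loss is confined to the numeric cap within subclinical hypothyroidism and to any programmed check that copies it; the documents do not say whether such a check exists. The pharmacokinetic precision figures, the sample size of 12 and the SAP analysis rules are untouched. Severity is low: a real error in an eligibility figure, cheap to correct, with limited consequences.

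**What to change.** 1. Check the source page of Protocol 6.1 to rule out a misread micro sign.
2. If the page reads as quoted, have the sponsor confirm the unit intended for the existing figure. If 10 was meant in mIU/L, equivalently microIU/mL, change the unit in 2j(iii) accordingly. No new threshold is proposed here.
3. Align the eligibility CRF and any programmed deviation check with the confirmed unit.
4. If anyone was enrolled under the written unit, review screening TSH against the confirmed limit, so that the deviation listings planned in SAP 7.2 rest on one criterion.

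The cost is a one-unit protocol correction, plus a matching edit check where one is used. No analysis, sample size or SAP text needs to change.
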